## **6.3. Alcohol, Nicotine and Drug Usage**

The following characteristics will be summarized based on ITT set, and repeated on Safety set:

- Alcohol status (never a drinker, current drinker, ex-drinker)
- Nicotine status (never smoked, smoker, ex-smoker)
- Drug status (never, current, former)

## **6.4. Genetic Analysis**

The following genetic analysis components will be summarized based on ITT set, and repeated on Safety set:

- CYP1A2 Genotype
- CYP1A2 Phenotype
- UGT1A1 Genotype
- UGT1A1 Phenotype

## 6.5. Medical History

Medical history will be coded using the Medical Dictionary for Regulatory Activities (MedDRA v21.0 or later). The number and percentage of patients with any medical history will be summarized overall and by treatment for each system organ class (SOC) and preferred term (PT). SOCs and PTs will be presented in a descending order of overall patient frequency, then the patient frequency within treatment groups from high dose to low dose and placebo group, if applicable.

Patient medical history data including specific details will be presented in a listing.

## 6.6. Prior and Concomitant Procedure

### 6.5.1. Prior Procedure

Procedures collected on the Prior and Concomitant Procedures eCRF pages will be coded to SOC and PT terms using MedDRA (v21.0 or later). The procedures with the date prior to the start of study drug (SKI-O-703 or placebo) will be counted as prior procedures. The number and percentage of patients who had any prior procedures will be presented, and summaries will be provided overall and by treatment for each SOC and PT.

A listing will be generated for all procedures (including prior and concomitant) collected.

### 6.5.2. Concomitant Procedure

The procedures with the date on or after the start of study drug (SKI-O-703 or placebo) will be counted as concomitant procedures. The number of patients having concomitant procedures will be summarized overall and by treatment for each SOC and PT.

## 7. Treatments and Medications

### 7.1. Prior and Concomitant Medications

Use of all concomitant medications that the patient is receiving at the time of Screening or receives during the study must be recorded in the patient's eCRF. All medications will be coded according to the World Health Organization Drug Dictionary (WHODD) Enhanced B3 March 2018 or later.

A prior medication is defined as any medication that has a stop date prior to the first dose of study drug (SKI-O-703 or placebo). Concomitant medications are defined as medications that are started between the first dose of study drug (SKI-O-703 or placebo) date and the last dose of study drug (SKI-O-703 or placebo) date, both inclusive, or started before the first dose of study drug (SKI-O-703 or placebo) date but ended or remain ongoing while on treatment. Incomplete medication start and stop dates will be imputed as per [Section 4.7](#).

The frequency table will be provided by treatment group and overall on ITT set. The number and percentages of patients who had any prior medications will be summarized overall and by treatment groups, therapeutic drug classes (ATC level 2) and generic drug names. Therapeutic drug classes and generic drug names will be presented in a descending order of overall patient frequency, then the patient frequency within treatment groups from high dose to low dose and placebo group, if applicable. Similar frequency tables will be provided for permitted concomitant medications and prohibited concomitant medications on ITT set. The prohibited concomitant medications are defined in protocol Section 5.8.3.

The list of prohibited concomitant medications should be reviewed and finalized by sponsor designee before final database lock.

A listing of prior and concomitant medications by patient will be provided, with an indicator to identify the prior and concomitant medications.

## 7.2. Rescue Medications

In case of bleeding events requiring rescue medication, the following rescue medications are permitted: IVIG 1 g/kg/day for 2 days (ie, 2 g/kg), romiplostim 2 to 5 µg/kg, dexamethasone 40 mg/day for 4 days, other high dose parenteral steroids (ie, solumedrol 1 g IV), platelet transfusions (these may be reserved for serious or life threatening bleeding events), or standard of care as per participating countries. Patients should be withdrawn in case of CNS bleeding or life-threatening GI bleeding (see protocol Section 4.2.1).

Rescue medications will be coded to therapeutic drug classes (ATC level 2) and generic drug names using WHODD Enhanced B3 March 2018 or later. The number and percentages of patients who had any rescue medications will be summarized overall and by treatment, therapeutic drug classes (ATC level 2) and generic drug names based on ITT set. Therapeutic drug classes and generic drug names will be presented in a descending order of overall patient frequency, then the patient frequency within treatment groups from high dose to low dose and placebo group, if applicable.

A listing with all rescue medications will be generated.

## 7.3. Prior Therapy

Therapies collected on the Prior Therapy eCRF pages will be coded to therapeutic drug classes (ATC level 2) and generic drug names using WHODD Enhanced B3 March 2018 or later. The number and percentages of patients who had any prior therapy will be summarized overall and by treatment, therapeutic drug classes (ATC level 2) and generic drug names based on ITT set. Therapeutic drug classes and generic drug names will be presented in a descending order of overall patient frequency, then the patient frequency within treatment groups from high dose to low dose and placebo group, if applicable.

A listing with all prior therapies will be generated.

#### **7.4. Study Treatments**

On Day 1, eligible patients will be randomly assigned to receive either SKI-O-703 200 mg BID, SKI-O-703 400 mg BID or placebo. SKI-O-703 200 mg BID, 400 mg BID, and placebo will be administered orally. On Day 1, the investigative site staff will administer the morning dose. The evening dose of study medication will be administered 12 hours after the morning dose. Patients will be administered the study medication with enough water to swallow the capsule. From Day 2 to Week 12, patients will self-administer study drug.

##### **7.4.1. Extent of Exposure**

Duration of exposure is defined as the total number of days a patient is exposed to study drug (SKI-O-703 or placebo) and will be presented as the total number of days from the first dose date (Day 1) to the last dose date (date of last dose minus the date of first dose + 1) as recorded on the End of Treatment page on the CRF.

The duration of exposure to study drug by treatment will be summarized for all patients in the Safety set and will be presented in a table by summary statistics. The duration of exposure will then be classified into one of the following categories: < 2 weeks, 2 to <4 weeks, 4 to <6 weeks, 6 to <8 weeks, 8 to <10 weeks, 10 to 12 weeks and will be presented as the number and percentage of patients in each duration category. Percentages will be computed from the number of patients in the Safety set.

##### **7.4.2. Treatment Compliance and Modifications**

Each patient's dosing schedule should be closely monitored by the site at each study visit. This will ensure that all patients enrolled into the study maintain their original dosing schedule beginning with the first dose of study drug.

Study drug compliance will be calculated for each patient by taking into account whether a patient takes all doses of study drug as instructed. The number of tablets taken will be calculated from subject dosing data in eCRF.

The overall study drug compliance (%) will be calculated by dividing the total number of tablets taken by the total number of tablets prescribed and then multiplying by 100.  
Compliance (%) = [(total no. of tablets taken) / (No. of days exposure × No. of tablets prescribed per day)] × 100

The overall study drug compliance will be summarized by treatment based on Safety set.

A patient is considered compliant if overall study drug compliance is between 80% - 120%.

Summary statistics on percentage of treatment compliance as well as the number and percentage of patients in each compliance category (<80%, 80%-120%, and >120% compliant) will be presented overall. Percentages will be calculated out of the number of patients who were dosed at that dosing period in the Safety set.

Patients drug accountability data will be provided in a listing.

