3.1.1 Dose Interruption and Reduction

It is recognized that some AEs may require dose adjustment or study drug discontinuation. Intra-subject dose reduction or escalation is permitted and based upon treatment-related adverse events observed ([Table 1](#)).

After experiencing an AE, subjects whose laboratory results return to baseline values and remain stable for 4 consecutive weeks have the option to increase the dose of SKI-O-703 1 dose level up to the randomized dose level.

Table 1 Guidelines for Dose Interruption or Reduction^a

AE	Occurrence	Action
ALT elevations (range 3 to 5 \times ULN) Alkaline Phosphatase > 3 \times ULN and > 2 \times baseline	First	
 If asymptomatic (no nausea, anorexia, vomiting), repeat test within 72 hours^b and, if stable or lower, may continue dosing of study drug. If on repeat test value has increased further but remains < 5 \times ULN and asymptomatic, withhold study drug and retest weekly until values becomes stable. When stabilized to < 5 \times ULN, continue dosing with the study drug. If symptomatic or > 5 \times ULN, withhold study drug. Follow the subject weekly until symptoms abate and values return to baseline per confirmation from central laboratory; at which time study drug may be restarted at a 50% reduced dose by taking only one daily dose. 
Note: Discontinue study drug permanently if the ALT elevation is accompanied by an elevation in direct bilirubin to > 2 mg/dL (34.2 mmol/L).

	Second	Discontinue study drug permanently.
ANC <1,000/mm ³ or febrile neutropenia	First	Withhold dose until ANC \geq 1000/mm ³ , or has returned to baseline, then reduce the dose by skipping one of the daily dose and increase to previous dose if ANC remains stable for 2 weeks on reduced dose.
	Second	Discontinue study drug permanently if the intolerance reoccurs or persists.
Sustained increased systolic (> 160 mmHg) or sustained increased diastolic (> 100 mmHg) blood pressure in a previously normotensive subject	First	
Study drug may be withheld for 5 to 7 days and then restarted at a reduced dose by skipping one of the daily dose.
 
Irrespective of study drug dose adjustment, subjects who develop a sustained increased systolic (>140 mmHg) or a sustained increased diastolic (>90 mmHg) blood pressure should be started on antihypertensive medications (e.g. lisinopril 5mg daily) or have their antihypertensive regimen adjusted if already on any antihypertensive agent.

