5.2 Treatments Administered

Subject specific doses will be prepared and checked by blinded pharmacy staff and administered by appropriately trained blinded clinic staff as delegated by the principal investigator at the study site. The study drugs will be identical in number and appearance for each group. The following dosing scheme will be performed:

- 200 mg BID group: 2 capsules of 100 mg SKI-O-703 + 2 capsule of placebo
- 400 mg BID group: 4 capsules of 100 mg SKI-O-703 + 0 capsules of placebo
- Placebo group: 4 capsules of placebo

SKI-O-703 200 mg BID, 400 mg BID, and placebo will be administered orally. On Day 1, the investigative site staff will administer the morning dose of study medication. The evening dose will be administered 12 hours after the morning dose. Subjects will be administered the study medication with enough water to swallow the capsules. The investigative site staff will check the subject's mouth to ensure the study drug and entire volume of water was swallowed. The study medication will be taken no later than 30 minutes after food. Subjects enrolled in the safety run in period will be admitted for 24 hours on Days 1, 8, and 84 or 85

of the study. Subjects selected for the PK/PD portion of the study will be admitted for 24 hours on Days 1 and 84 or 85 of the study. The subject will be instructed to self-administer the subsequent doses of the study medication in the morning and evening (12 hours after the morning dose) for the remaining study duration.

Dosing of the study medication that occur on study visit days, subjects will take the morning dose of study drug in the office under the guidance of study site personnel after all specified study tests and procedures have been completed. However, if the visit cannot be scheduled in the morning, the subject will be instructed to take the morning dose at the regular schedule on that visit day.

Each subject's dosing schedule should be closely monitored by the site at each study visit. This will ensure that all subjects enrolled into the study maintain their original dosing schedule beginning with the first dose of study drug.

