##### **4.6.3. Per-protocol (PP) set**

The PP set will consist of all patients in ITT set with no major protocol violations that may impact the analysis. Major protocol violations will be identified during the study according to the protocol deviation list and treatment compliance defined in [Section 7.4.2](#). Patients will be analyzed according to the treatment arm to which they were randomized. This analysis set will be used for efficacy summaries, including the analysis of the primary endpoint.

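### The SAP 7.4.2 compliance formula keeps directed hold days in the denominator and leaves the prescribed number undefined after a directed reduction, so some patients who follow Table 1 exactly can score below 80%

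*SAP*

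**What the plan says.** SAP 7.4.2 introduces compliance as "taking into account whether a patient takes all doses of study drug as instructed". The displayed equation divides the number taken by "No. of days exposure × No. of tablets prescribed per day". The section then sets the band: "A patient is considered compliant if overall study drug compliance is between 80% - 120" percent. Its title mentions modifications, but it contains no rule for held or reduced doses.

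SAP 7.4.1 defines days of exposure as the "total number of days from the first dose date (Day 1) to the last dose date", that is, "date of last dose minus the date of first dose + 1". Interruptions are not subtracted.

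Protocol 3.1.1, Table 1, directs both interruptions and reductions to one of the two daily doses. For example, after one type of ALT event "study drug may be restarted at a 50% reduced dose by taking only one daily dose". Other rows give holds of 5 to 7 days, holds of up to 14 days, and holds that last until a laboratory value recovers. One QTcF row keeps the reduced dose to the end of the study.

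SAP 4.6.3 identifies major violations for the PP set "according to the protocol deviation list and treatment compliance defined in" Section 7.4.2. It restricts exclusion to violations that could affect the analysis. SAP 8 runs the efficacy analyses on the ITT set and repeats them on the PP set.

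**The concern.** The stated aim of SAP 7.4.2 is to measure whether the patient took the doses they were told to take. The equation measures something else. When a hold is followed by a restart, every held day adds a full day's capsules to the denominator, although the instruction on that day was to take none. After a directed reduction, the text does not settle whether the prescribed number is the randomized 8 capsules a day or the reduced number.

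Two things are at stake. The compliance table may label as non-compliant patients who did what the protocol told them. And because SAP 4.6.3 draws on the same figure, those patients may be left out of the PP repeats for a reason that arises after randomization and is tied to adverse events. Two programmers could also read the term differently and build two different PP sets. With 24 patients per active arm and 12 on placebo, each exclusion removes 1/24 = 4.2% or 1/12 = 8.3% of an arm.

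**Working it through.** **Inputs.** Each dose is 4 capsules in every arm (Protocol 5.2, for example "Placebo group: 4 capsules of placebo"), taken twice daily, so 8 per day. The SAP says tablets; the product is capsules. Treatment lasts 12 weeks = 84 days (Protocol 3.1), so the full denominator is 84 × 8 = 672. The band is 80% to 120% (SAP 7.4.2). Hold and reduction patterns come from Table 1. The documents give no event onset days, so those below are illustrative. The patient is assumed to follow each instruction exactly.

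The plan states no compliance figure to reproduce. Its one related number, 82.7% power for 24 versus 12 at 50% versus 1%, reproduces with a pooled-variance normal approximation with continuity correction (82.73%). It does not involve compliance or the PP set.

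**Reading A: the prescribed number stays at 8 per day.**

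Hold of h days, then full dose: compliance = (84 − h)/84. Lasting half dose after Day d, no hold: (8d + 4(84 − d))/672 = (84 + d)/168.

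| Path over 84 days | Calculation | Compliance |
|---|---|---|
| 7-day hold only | 77/84 | 91.7% |
| 14-day hold only | 70/84 | 83.3% |
| 16-day hold only | 68/84 | 81.0% |
| 17-day hold only | 67/84 | 79.8% |
| Half dose to end after Day 28 | 112/168 | 66.7% |
| Half dose to end after Day 50 | 134/168 | 79.8% |
| Half dose to end after Day 51 | 135/168 | 80.4% |
| 7-day hold after Day 28, then half dose to end | (224 + 196)/672 | 62.5% |
| 7-day hold, 28 days half dose, return to full | (672 − 56 − 112)/672 | 75.0% |
| 7-day hold, 14 days half dose, return to full | (672 − 56 − 56)/672 | 83.3% |

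**Reading B: the prescribed number falls to 4 per day after a reduction, but held days still count at 8.** This is the favourable reading of the reduction. Held days remain because SAP 7.4.1 counts them as exposure. Compliance = taken/(taken + 8h).

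| Path | Calculation | Compliance |
|---|---|---|
| 7-day hold after Day 28, then half dose to end | 420/(420 + 56) = 420/476 | 88.2% |
| 14-day hold after Day 28, then half dose to end | (224 + 168)/(392 + 112) = 392/504 | 77.8% |
| 14-day hold after Day 7, then half dose to end | (56 + 252)/(308 + 112) = 308/420 | 73.3% |
| 14-day hold then full dose, 42 days of exposure in all | 224/336 | 66.7% |

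The second and third rows follow the confirmed-QTcF path of Table 1 at its longest hold. The last row involves no reduction, so it is the same under both readings. It can arise from the ALT row that resumes dosing once values have stabilized.

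**If the denominator is the sum of capsules instructed each day** (0 on held days, 4 on reduced days, 8 otherwise), every path above gives 100%.

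**The case against.** The strongest reply is that the text can be read benignly. SAP 7.4.2 refers to doses taken as the patient was told, and its verbal definition divides by the total number prescribed; after a reduction, that total would naturally be the reduced number. This stands as far as reductions go: the 66.7% and 79.8% half-dose figures under Reading A depend on the other interpretation. It does not cover holds, because the displayed equation multiplies all days from first to last dose by a daily number, and the 77.8%, 73.3% and 66.7% figures under Reading B follow from that.

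A reader might infer several stronger things that the documents do not support:

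- **That patients who follow Table 1 generally fall below 80%.** They do not. Over 84 days, holds of 16 days or less alone, a 7-day hold with two weeks at half dose, and late reductions all stay at or above 80%, even under Reading A. The 17-day mark is beyond Table 1's fixed-length holds. It can be reached only where a hold has no maximum (ALT, ANC), and no expected duration is given for those.
- **That a score below 80% removes a patient from the PP set automatically.** SAP 4.6.3 does not say so. It combines compliance with the deviation list and requires that the violation could affect the analysis.
- **That the loss falls mainly on the active arms because of toxicity.** Table 1 applies to all blinded arms and no dose-modification rate by arm is given. Allocation alone puts 48/60 = 80% of patients on active drug. A higher active rate is plausible, since Table 1 is built on events seen with a drug of similar mechanism. But the multiple-dose healthy-subject study in Protocol 1.1 reports any TEAE in 27.8% on active and 33.3% on placebo.

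It can also be argued that a patient at half dose for most of treatment no longer represents the randomized regimen and may reasonably be left out of a PP analysis. That is a legitimate choice of estimand. It should be made openly, not as a by-product of an undefined term.

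**Conclusion.** The point holds in limited form. The formula keeps directed hold days in the denominator at the full prescribed number and is silent on the prescribed number after a directed reduction, against the section's own stated aim. Some patients who follow Table 1 exactly can score below 80% on either reading: 77.8% for a 14-day hold after Day 28 then half dose with the prescribed number lowered, and 66.7% for a 14-day hold within 42 days of exposure. If the number stays at 8 per day, any lasting half dose starting after Day 50 or earlier also falls below 80%.

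The effect is confined to the compliance summary and the PP repeats. Affected patients may be labelled non-compliant and may be excluded; how many, and from which arms, cannot be derived from the documents, so neither the size nor the direction of any bias is established. The results assume exact adherence, 84 days of exposure unless stated otherwise, and illustrative onset days.

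**What to change.** In SAP 7.4.2, replace the denominator with the sum over exposure days of the capsules instructed on that day: 0 on days of directed hold, the reduced number after a directed reduction, and 8 otherwise.

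In SAP 4.6.3, state whether compliance outside 80% to 120% on that measure is by itself a major violation.

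Separately, and before unblinding, the sponsor should state whether patients with long directed reductions belong in the PP set. Either answer can be defended once written down.

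The cost is SAP wording and a change to one derivation. SAP 7.4.2 already takes the number of doses taken from eCRF dosing data. The programmer must also be able to identify the dates of directed holds and reductions. No dosing rule, primary analysis or sample size changes.

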## 8. Efficacy Analysis

The results for each efficacy endpoint will be summarized by treatment for all patients within the ITT set using descriptive statistical methods, and repeated within the PP set. Continuous variables (quantitative endpoints) will be summarized using the mean, the standard deviation (SD), median, range (minimum value and maximum value), and interquartile. Categorical variables (qualitative endpoints) will be summarized using frequency counts (number) and percentages. Data will be listed in data listings.

All statistical tests will be 2-sided using a 5% significance levels, leading to 95% (2-sided) confidence intervals (CIs). This will be used for each pairwise comparison with placebo, ie, there will be no adjustments for multiplicity since this is a Phase 2 study, and interim analysis will only be performed on safety and PK analysis.

If there are multiple post-baseline platelet count results in the same visit, the result from central lab will be used first. If there are more than one central lab result in the same visit, the result with larger platelet count will be used. However, if only local lab results exist, the local lab result with larger platelet count will be used.

